Aim 3. Investigate the longitudinal effects of CogSMART-PD on cognition, neuropsychiatric symptoms and quality of life / health status in individuals with PD-MCI.

Hypothesis 3: Compared with the supportive care control group, CogSMART-PD participants will demonstrate less cognitive decline, fewer neuropsychiatric symptoms, and better QoL/HS at the 6- and 12-month follow-up assessments.

Exploratory Aim 1: To examine neural changes associated with the performance on an fMRI executive function task following participation in CogSMART.

Exploratory Hypothesis 1: Compared to the non-intervention/waitlist PD participants, CogSMART completers will evidence a reduction in the dorsolateral prefrontal gyrus (due to increased cognitive efficiency) during an fMRI task of executive functioning.

Exploratory Aim 2: To investigate the feasibility and efficacy of improving visual-spatial cognition by using the Wii as an adjunct to CogSMART.

Exploratory Hypothesis 2: Compared to CogSMART (without Wii) completers, participants who use Wii as an adjunct to CogSMART (CogSMART+Wii) will demonstrate greater gains in visual spatial cognition.

Exploratory Aim 3: To investigate the feasibility and efficacy of improving visual-spatial cognition and motor skills by participating in Odoroki (computer program performing physical activity to music) as an adjunct to CogSMART.

Exploratory Hypothesis 3: Compared to CogSMART (without Odoroki) completers, participants who practice Odoroki as an adjunct to CogSMART (CogSMART+Odoroki) will demonstrate greater gains in visual spatial cognition and motor skills.

Exploratory Aim 4: To investigate changes in neuroinflammatory biomarker (cortisol, CRP, DHEA, and alpha-amylase) levels pre- and post-treatment for intervention and control participants.

Exploratory Hypothesis 4: Compared to the supportive care control group, CogSMART-PD participants will show a reduction in neuroinflammatory biomarker levels and this reduction will be associated with cognitive improvement.

Exploratory Aim 5: To investigate in the association between Brain-derived Neurotrophic Factor (BDNF) gene expression levels and cognitive change pre- to post- intervention.

Exploratory Hypothesis 5: BDNF gene expression levels will be associated with greater cognitive improvement following the CogSMART-PD intervention compared to the control condition.

Exploratory Aim 6: Investigate mediators of CogSMART-PD treatment effects.

Section 7 - Background and Significance

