Participants: 110 patients (55 per group) with PD-MCI will be recruited for this study as well as 110 identified and consistent caregivers of the participants. All caregivers will be asked to complete several questionnaires regarding the participant's quality of life and daily functioning prior to the intervention, at follow-up visits, and after the intervention. Although attrition did not occur in Phase I, over-recruitment by 20% will be instituted to account for possible subject attrition or unusable data. Participants will receive a payment of \$40 for each of the four assessments they complete (pre- and post-intervention/support and 6- and 12-month follow-ups).

Procedures: We will primarily recruit Veterans with PD from the VASDHS Neurology and Neuropsychology Clinics. While we will attempt to exhaust recruitment at VA clinics first, recruitment of women may be limited at the VA, and therefore, we will likely need to recruit from outside clinics to obtain a PD-epidemiologically accurate gender ratio of 60 (men)/40 (women). In this regard, we will primarily recruit from the University of California, San Diego (UCSD) Movement Disorders Center. Referred participants will be screened for inclusion/exclusion criteria (please see above) and consented if appropriate. All participants will have Level II MDS-criteria based diagnosis of MCI derived from a formal neuropsychological evaluation within the past 12 months. As most participants will be referred from the VASDHS and UCSD Movement Disorder Center, the majority will have MDS-criteria MCI diagnoses prior to referral. However, should a PD patient be referred for this study who has not had formal neuropsychological testing or if testing is outdated (>12 months), pre-inclusion neuropsychological testing will be performed through [name] lab, which follows patients neuropsychologically. Likewise, if the WRAT-4 Reading scale has not been administered within the past year, this 2-5 minute measure will also be administered to ensure adequate reading level. To avoid confounds, no test proposed as outcome measures in this study will be used to determine the PD-MCI diagnosis.

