The Unified Parkinson's disease Rating Scale - Part III (UPDRS-Part III)^{75, 76} and the modified Hoehn and Yahr Rating Scale (HYRS)^{77, 78} will be used to assess level of motor impairment and disease severity. For this assessment participants go through a series of tasks designed to assess various motor characteristics such as speech, facial expression, rigidity, finger tapping, hand movements, toe tapping, freezing of gait, balance, etc. We will also use UPDRS item #13 to assess fall risk (please see Monitoring Plan below). These are standard instruments for measuring the motor symptoms and disease severity in patients with PD and have been used extensively in both research and clinical settings. VASDHS/UCSD neurologists will perform these assessments immediately prior to the cognitive assessment at the pre and 12-month follow up evaluations.

Adjunct Performance Measures:

Motor Skill Fitness measures will be carried out by a trained research assistant at the VA Medical Center

Subjects will undergo body mass index analysis at the VA Medical Center

De-identified data from these Motor Skill Fitness measures will be analyzed in the Smart Lab at UC San Diego. No participant data will be collected there.

Client Satisfaction with the intervention will be assessed at the end of the intervention with the Client Satisfaction Questionnaire (CSQ-8)⁷⁹. The CSQ-8 is an 8-item, 2-3 minute measure that yields a single score, ranging from 8 to 32 (each item rated on a 4-point Likert scale), with higher scores indicating greater satisfaction. The CSQ-8 has been widely used in clinical research trials and is reported to have excellent reliability and internal consistency, acceptability to clients and service providers, and sensitivity to different levels of program quality.

Intervention: The treatment intervention is CogSMART-PD. Participants will meet in groups of 5 individuals per group for 1.5 hours once per week for 10 weeks.

Control Group: The supportive care (control) group will entail having groups of 5 individuals with PD-MCI meet for peer-support for 1.5 hours once per week for 10 weeks. A trained clinician will serve as the facilitator of this group and will be instructed to not provide any treatment or intervention strategies. The main role of the facilitator will be to create a safe and respectful environment where members feel comfortable sharing their knowledge and insight with each other.

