fMRI task and analysis: Participants will undergo fMRI while performing the Matrix Reasoning task (f-MRT), a well-developed and normed test of executive functioning for fMRI (Allen & Fong, 2008). Within the scanner, participants will be presented with 4 practice items followed by 24 test stimulus items and 24 alternative stimuli, conceptually modeled after problems found on the Raven's Progressive Matrices test, as well as items from the matrix reasoning subtest of the WAIS-III, collectively called the f-MRT (Allen and Fong, 2008). Each stimulus consists of a 3×3 matrix of complex visual figures, with one figure missing. For each matrix problem, participants will be instructed to "indicate what the missing figure should be," and to then select it from among the four choice alternatives presented on the right side of the matrix. Participants will also be told to place more importance on response accuracy than on response speed. Accuracy (% correct) and reaction time will be measured.

Each participant's scanning session will last approximately one hour, during which an anatomical scan and two functional scans will be run while performing the tasks. An 8-channel brain array coil during a series of T2* weighted EPI scans acquired to measure BOLD functional activity will be used. The parameters for the EPI scans will be: 64x64 matrix, $3.43 \times 3.43 \times 2.6$ mm voxels with 1.4 mm gap, TR = 2 seconds, TE = 32 ms, flip angle of 90 degrees, and 30 slices. These parameters will cover the entire brain. The acquisition of the EPI scans will be performed in the axial plane. Tasks are synchronized with the scanner using a TTL pulse sent to a laptop computer.

As secondary exploratory aim, we will recruit 8-10 additional individuals to participate in 10, 30-minutes of Wii training (tennis, golf, and ping pong games) in addition to the CogSMART program. These individuals will be assessed with the same procedures as described for the CogSMART (without Wii) participants.

As an additional exploratory aim, we will recruit 8-10 individuals to participate in 20, 1 hour-long Odoroki sessions where the individuals will perform physical activities to music by using a computer program. These individuals will be assessed with the same procedures as described for the CogSMART participants without an adjunct exercise program.

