PD participants may gain cognitive improvement and/or a delay in cognitive decline over time resultant from participating in this study with the additional scientific benefit of understanding the kinds of non-pharmacologic interventions that may aid cognition in PD with cognitive impairment and/or dementia. Study participants will be provided with a CogSMART manual. Those individuals in the wait-list control group will be offered the cognitive treatment at the completion of the intervention period if they are interested. There will not be any direct benefit to the caregivers, however, the investigator and associates may learn more about how participation in a cognitive skills training course impacts the function and quality of life of individuals with Parkinson's disease. Additionally, we may learn if caregivers of individuals with Parkinson's disease may benefit indirectly (e.g., improvement in caregiver's quality of life) from the group participant's (e.g., spouse, relative, friend's) participation in the intervention.

Inclusion of Women and Minorities: No exclusions will be made based on gender, race or ethnic background. Gender and ethnic composition of the samples will reflect that of the population of eligible patients presenting from the recruitment sources.

Phase II:

We will recruit 110 individuals with Parkinson's disease (PD) and Mild Cognitive Impairment (PD-MCI) primarily from the VA San Diego Healthcare System (VASDHS) Neurology and Neuropsychology Clinics, as well as 110 identified and consistent caregivers (e.g., spouse, friend, relative) of the participants to complete several questionnaires regarding the participant's quality of life and daily functioning prior to the intervention, during follow-up visits, and after the intervention. However, as recruitment of women may be limited at the VA, we may need to recruit women outside of the VA to obtain a PD-epidemiologically accurate gender ratio of 60 (men)/40 (women). We will plan to recruit from the University of California,

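### The Wii and Odoroki efficacy hypotheses cannot be answered by small, unrandomised groups with unmatched extra contact, and the plan should place add-on recipients outside the main comparison

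*Combined protocol and SAP*

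**What the plan says.** Section 6 (Specific Aims, Phase II) asks in Exploratory Aims 2 and 3 about both the feasibility and the efficacy of adding Wii or Odoroki to CogSMART. Exploratory Hypothesis 3 reads: "Compared to CogSMART (without Odoroki) completers, participants who practice Odoroki as an adjunct to CogSMART (CogSMART+Odoroki) will demonstrate greater gains", in visual-spatial cognition and motor skills. Hypothesis 2 makes the parallel claim for Wii, in visual-spatial cognition only.

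Section 9 (Design and Methods, Phase II) sets up the add-ons in two sentences. For Wii: "we will recruit 8-10 additional individuals to participate in 10, 30-minutes of Wii training". For Odoroki: "we will recruit 8-10 individuals to participate in 20, 1 hour-long Odoroki sessions". Both groups are assessed in the same way as CogSMART participants without an add-on.

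On the main comparison, Section 9 says "110 patients (55 per group) with PD-MCI will be recruited for this study", and these patients are allocated to CogSMART-PD or Supportive Care. CogSMART-PD participants attend as follows: "Participants will meet in groups of 5 individuals per group for 1.5 hours once per week for 10 weeks". Control groups "meet for peer-support for 1.5 hours once per week for 10 weeks". No add-on is described for supportive care.

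**The concern.** The hypotheses are comparative: people with an add-on should gain more than people without one. To attribute such a difference to Wii or Odoroki, the two sets of people should be alike apart from the programme. The plan makes them differ in how they entered, in hours of supervised contact and, because the comparator is completers, in having finished the course. If the plan is followed exactly and a difference appears, there is still no basis for calling it efficacy of the add-on.

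A smaller issue is bookkeeping. The plan does not say whether add-on recipients are counted in the 55 per arm. If they were, one arm alone would contain people doing extra exercise, and the main comparison would not be of CogSMART-PD alone.

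**Working it through.** **How people reach each group.** Section 9 allocates two conditions only, CogSMART-PD and Supportive Care. For the Phase II fMRI sub-study it states random assignment, 30 to each group. For Wii and Odoroki it says only that people will be recruited. Sections 10.5 and 12.1d describe a consent step specific to the adjunct programmes. Entry to an add-on is therefore by recruitment and choice.

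**Contact hours** (sessions × length, all from Section 9):
- CogSMART-PD: 10 × 1.5 = 15 h
- Supportive care: 10 × 1.5 = 15 h
- CogSMART plus Wii: 15 + 10 × 0.5 = 20 h, and 20/15 = 1.33
- CogSMART plus Odoroki: 15 + 20 × 1 = 35 h, and 35/15 = 2.33

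The two main arms are matched on contact. The add-on comparisons are not.

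**Precision.** The plan gives no alpha, power, effect size or SD, so there is no calculation behind 8-10 to reproduce. Assume a two-sided 5% test, 80% power, SD = 1, and all 55 CogSMART-PD participants as completers, which is generous. The detectable standardised difference is (1.96 + 0.84) × √(1/n + 1/55):
- n = 8: 1.06
- n = 10: 0.96

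Under the same assumptions, power is 26-31% at d = 0.5 and 56-64% at d = 0.8. If 10 recipients came out of the 55 (10 v 45), the detectable d is 0.98.

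**Outcomes.** The cognitive measures listed for Phase II in Section 9 include no dedicated visuospatial test; the nearest item is clock drawing within the PD-CRS. The UPDRS motor examination is scheduled at baseline and 12 months only, and the motor fitness measures have no stated timing.

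**Where add-on recipients sit.** The passages side by side:
- The fMRI and Wii recruits are each called additional; the Odoroki recruits are not.
- The lay summary (Section 5) says only that some participants will be asked to do an add-on, which can be read as a subset.
- Section 10 gives 110 PD-MCI patients for Phase II but also omits the 60 additional fMRI recruits, so it is not a full list and places no one.
- Totals do not settle it. Section 2a plans 350 consented subjects and Phase I takes about 240, leaving 350 − 240 = 110. Phase II patients and caregivers alone are 110 + 110 = 220.

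If all 8-10 Odoroki recipients were inside the CogSMART-PD arm, they would be 8/55 = 14.5% to 10/55 = 18.2% of it. Any resulting bias would be that share times the effect of Odoroki on Matrix Reasoning, the primary outcome. The documents give no value for that effect, so no size is put on the bias.

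**The case against.** The aims are labelled exploratory, include feasibility, and support no confirmatory claim or decision. Small, unrandomised add-on groups are ordinary in pilot work, and 8-10 people can inform feasibility. This stands, and it is why the aims should be kept in reduced form. But the exploratory label excuses low power; it does not make a comparison of self-selected people with more contact into a test of the programme.

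A reader might go further and infer that the primary comparison is confounded by the add-ons. The documents do not support that. Wii recruits are additional. The Odoroki sentence follows directly after the Wii one and contrasts its recruits with CogSMART participants who have no add-on, which leans towards a separate group. No timing is given for the Odoroki sessions, so they may not precede the 10-week assessment. The Odoroki hypothesis concerns visual-spatial and motor outcomes, not Matrix Reasoning. What remains is an open question about Odoroki membership. The missing word and the loose lay summary allow the inside reading. So does the saliva aim: it too recruits 8-10 people without calling them additional, and its hypothesis compares the two main arms.

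**Conclusion.** The efficacy part of Exploratory Aims and Hypotheses 2 and 3 has no answer in this design. That rests on the allocation, consent and contact provisions alone: 5 h (Wii) or 20 h (Odoroki) of unmatched contact on top of 15 h, with entry by choice. The precision figures are secondary and depend on the stated assumptions. Feasibility remains answerable.

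On the main comparison, the finding is a missing statement, chiefly for Odoroki. It is not a demonstrated bias.

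**What to change.** 1. In Sections 6 and 9, restate Exploratory Aims and Hypotheses 2 and 3 as feasibility (attendance, completion, safety) with descriptive pre-post change. Remove the efficacy wording and the claim of greater gains than CogSMART completers.
2. In Section 9, state that Odoroki recipients, and confirm that Wii recipients, are recruited outside the 55 per arm and enter no CogSMART-PD versus supportive-care comparison. Align the lay summary with this.
3. If any recipients were already allocated within the 110, keep the primary analysis by allocation, report how many there are, and add a sensitivity analysis without those individuals. Note its limit: it removes people who chose an add-on from one arm only, so the remaining groups are no longer the allocated ones.

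The cost is a few sentences and one analysis flag. The loss is an add-on efficacy claim that the design could not support.

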9.12) Describe each off-station activity including where it occurs, subject involvement, and any additional required protections. Note: if the off-station activity is being conducted under the approval authority of another institution, this is not VA offsite research and should be described as collaborative research effort. Please contact the HRPP office if you have any questions

Phase I:

100 participants will be scanned at the UCSD Keck Center for fMRI.

Participants who consent to do so will participate in a home evaluation conducted within their home. One form which assess the home environment will be used for this assessment (please see appended form). All data collected during the home visits will only be identified by a subject ID number that is assigned during the consent process.

Phase II:

Up to 60 individuals may be scanned at the UCSD Keck Center for fMRI.

De-identified data from Motor Skills Assessments will be analyzed by collaborators in UC San Diego's Smart Lab, located in Atkinson Hall, 5202. No participant data will be collected at the Smart Lab.

De-identified saliva samples will be stored and analyzed by the UCSD Integrative Health and Mind-Body Biomarker Laboratory, located at the Medical Teaching Facility, Room 431. Samples are destroyed after analysis.

Section 10 - Human Subjects

10) Describe the characteristics of the proposed subject population. Include age, gender, ethnicity, and health status as appropriate. Note: Data about people are still considered "human subjects" by the IRB, so even if you do not intend to contact the patients whose charts you will review, you still describe the characteristics related to the subjects whose charts you will review.

- **Provide inclusion and exclusion criteria as appropriate. Provide a statement how non pregnancy is confirmed if pregnancy is an exclusion criteria.**
- **For multisite studies, provide the total number of subjects from all sites and include description of the local site's role as a coordinating center if applicable.**
- **Indicate the number of VA participants to be studied.**
- **Indicate the estimated number of consented subjects that will fail the screening process, if any.**

Phase I:

Approximately 240 subjects in total will be recruited for this study: 20 PD patients to participate in CogSMART only (no imaging), up to 100 PD patients to participate in CogSMART and the imaging protocol, and 120 caregivers. The PD patients will range in age from 55-95. No patients under 55 will be imaged.

One hundred twenty individuals who have PD and documented cognitive impairment will be recruited from ongoing studies of neuropsychological functioning in PD (PI [name]). Over-recruitment by 10% will also be instituted to account for subject attrition or unusable data and to ensure a final sample size of 20 participants (10 per treatment and 10 per wait list group) for Aims 1 and 2 and up to 100 participants for the Exploratory Aim. All PD participants will be screened and excluded if they have a history of significant head trauma, other neurologic or major psychiatric disorders, history of developmental learning disorder, substance dependence, or any contraindication to participating in the cognitive treatment. PD patients must be medically/clinically stable in order to be included in this study. The participant's Parkinson's disease diagnosis will be confirmed by the participating neurologists, and cognitive impairment (i.e., MCI or dementia) will be confirmed via neuropsychological testing and the consensus of the neuropsychologist investigators (Drs. [name] and [name]). We will also recruit any identified and consistent caregivers (e.g., spouse, friend, relative) of the participants to complete several questionnaires regarding the participant's quality of life and daily functioning prior to and following (immediately, 3- and 9-months) the intervention. All caregivers will be asked to participate if they do not have any known memory impairment, dementia, or another condition which would prevent them from accurately completing the questionnaires.

PD participants may gain cognitive improvement and/or a delay in cognitive decline over time resultant from participating in this study with the additional scientific benefit of understanding the kinds of non-pharmacologic interventions that may aid cognition in PD with cognitive impairment and/or dementia. Study participants will be provided with a CogSMART manual. Those individuals in the wait-list control group will be offered the cognitive treatment at the completion of the intervention period if they are interested. There will not be any direct benefit to the caregivers, however, the investigator and associates may learn more about how participation in a cognitive skills training course impacts the function and quality of life of individuals with Parkinson's disease. Additionally, we may learn if caregivers of individuals with Parkinson's disease may benefit indirectly (e.g., improvement in caregiver's quality of life) from the group participant's (e.g., spouse, relative, friend's) participation in the intervention.

Inclusion of Women and Minorities: No exclusions will be made based on gender, race or ethnic background. Gender and ethnic composition of the samples will reflect that of the population of eligible patients presenting from the recruitment sources.

Phase II:

We will recruit 110 individuals with Parkinson's disease (PD) and Mild Cognitive Impairment (PD-MCI) primarily from the VA San Diego Healthcare System (VASDHS) Neurology and Neuropsychology Clinics, as well as 110 identified and consistent caregivers (e.g., spouse, friend, relative) of the participants to complete several questionnaires regarding the participant's quality of life and daily functioning prior to the intervention, during follow-up visits, and after the intervention. However, as recruitment of women may be limited at the VA, we may need to recruit women outside of the VA to obtain a PD-epidemiologically accurate gender ratio of 60 (men)/40 (women). We will plan to recruit from the University of California,

San Diego (UCSD) Movement Disorders Center as well as from additional sites (e.g., PD Association of San Diego, San Diego hospitals, private clinics, and the community). Participants will be included who are > 40 years of age, as < 40 years of age may represent a different form of PD. Participants will generally fall within the age range of 60-80 due to the prevalence of PD in these groups; however, no upper age limit or gender restrictions will be applied for this study.

Inclusion criteria: (1) Clinical diagnosis of PD based on the UK Brain Bank Criteria⁵⁹ (2) Clinical diagnosis of MCI based on formal criteria set forth by the Movement Disorders Society (MDS) Task Force⁵, and 3) >40 years of age (due to likelihood that individuals <40 may represent a different form of PD than idiopathic PD). The PD diagnosis will be confirmed by one of the VASDHS/UCSD neurologists. The MCI diagnosis will be confirmed by a licensed clinical neuropsychologist (Drs. [name] or [name]). Level II MDS Task Force criteria is as follows: (1) cognitive decline reported by the patient or caregiver or observed by a clinician, (2) cognitive deficits not severe enough to significantly interfere with functional independence, and (3) cognitive deficits on formal neuropsychological testing including two tests for each of five domains: Attention, Language, Memory, Executive Function, and Visuospatial Ability⁵. As per MDS criteria, cognitive deficits will be determined by impairment (i.e., 1.5 standard deviations below appropriate norms) on either two tests in one cognitive domain or on one test in two different cognitive domains.

Exclusion criteria: (1) Secondary causes of Parkinsonism (e.g., corticobasal degeneration, progressive supranuclear palsy, multiple systems atrophy, drug-induced parkinsonism, etc.); (2) other neurological conditions (e.g., stroke); (3) normal or dementia diagnosis via neuropsychological testing and based on the MDS criteria for PD dementia; (4) psychosis, antipsychotic treatment or treatment for substance abuse; (5) untreated current major depression disorder or anxiety disorder; (6) uncorrected vision or hearing to adequately read the manual and hear intervention facilitator; and (7) reading level below an eighth grade level determined by a standardized reading test (Wide Range Achievement Test 4 - Reading [WRAT-4]⁶⁰), as the intervention involves reading. In order not to overly restrict our sample and as almost all PD patients will be on some form of dopaminergic replacement therapy and various other medications for cognitive and mood symptoms (e.g., SSRIs), we will not exclude patients based on medications. However, we will ensure that participants are stabilized on medications by recruiting those patients who have not had any major changes in medications (i.e., PD medication regimen or antidepressant dosages) within 30 days of baseline testing and not including data in our analyses from any patient who had medication changes during the course of the treatment. We recognize that certain medications can worsen cognition, such as anticholinergic agents, amantadine, dopamine agonists and benzodiazepines⁶¹. Therefore, we will carefully document all medication types and dosages at each testing session and control for these in statistical analyses as needed. It is also recognized that medication changes may occur during and after the intervention. We will diligently record this changes and account for them in the analyses accordingly (e.g., as covariates).

There will not be any direct benefit to the caregivers, however, the investigator and associates may learn more about how participation in a cognitive skills training course impacts the function and quality of life of individuals with Parkinson's disease. Additionally, we may learn if caregivers of individuals with Parkinson's disease may benefit indirectly (e.g., improvement in caregiver's quality of life) from the group participant's (e.g., spouse, relative, friend's) participation in the intervention.

We expect no subjects once consented to fail the screening process.

Section 10.1 Non-Veteran Subjects

10.1a) Recruitment of non-Veterans cannot be for the sake of convenience for this study. Provide the objective and justification for the inclusion of non-Veteran subjects. Identify how the research results will be generalizable to the Veteran population. Identify the approximate number of non-Veterans who will be enrolled.

Phase I:

Most participants will be recruited from ongoing studies of neuropsychological functioning in PD (PI [name]) which recruits both veteran and non-veteran participants.

In addition to recruiting patients within the VASDHS, subjects will also be referred to us through clinics at UCSD because the number of patients at the VASDHS is not sufficient alone to meet our enrollment requirement. Currently there are over 350 PD patients being followed clinically in the Neurology Service at the VASDHS and the UCSD Movement Disorders Clinics. VA neurologists follow approximately 150 PD patients at the VASDHS and, approximately 200 patients at UCSD. Roughly two-thirds of their new patient evaluations are for PD patients at varying stages of the disease. For both the VASDHS and UCSD clinics, about 40% of the patients currently being followed would likely meet the inclusion criteria for the proposed project, which would result in about 140 patients being eligible for the study, of those 140 about 50% will have the necessary availability and schedule that can allow them to come to the VA weekly for

12 weeks and undergo two fMRIs. There is also a 5%-10% exclusion for participants unwilling and/or unable to undergo MRIs for various reasons (claustrophobia, metal in eyes/head, physical restrictions). Thus, in total, there are roughly 60-70 potential patients being followed continuously by the Movement Disorder specialists at the VA and UCSD (note this figure does not take into account potential new patient evaluations that will occur during the first year of recruitment).

PD patients will be referred from outside of the VA to meet enrollment criteria within the study period. It is often the case that PD patients within the VA have multiple other risk factors associated with cognitive decline including histories of substance abuse, head injury, and psychiatric conditions that would preclude them from participating in our study. They also fMRI limiting factors, such as shrapnel in their bodies that exclude them from participation in fMRI. Thus, additional non-veteran subjects from UCSD will be studied as needed.

Caregiver participation is necessary to measure the Parkinson's disease participant's quality of life. The caregivers enrolled in the study may be non-Veterans.

Phase II:

We will primarily recruit Veterans with PD from the VASDHS Neurology and Neuropsychology Clinics. While we will attempt to exhaust recruitment at VA clinics first, recruitment of women may be limited at the VA, and therefore, we will receive referrals from outside clinics to obtain an epidemiologically accurate gender ratio of 60 (men)/40 (women). In this regard, we will primarily recruit from the University of California, San Diego (UCSD) Movement Disorders Center. The VASDHS/UCSD neurologists follow approximately 600 PD patients in the VASDHS clinics and approximately 600 PD patients within the UCSD Movement Disorders Clinic. Should it be necessary, we will recruit outside of the VA and UCSD, including recruiting from the Parkinson's Association, San Diego area hospitals and clinics (e.g., Scripps and Sharp Healthcare Systems) who serve PD patients, private practices, and the community. It is estimated that there are 16,000-19,000 individuals living with PD in the San Diego area, of whom half are members of PASD. Our study team has ample experience recruiting from the community, including the use of flyers, tables at community-based events (e.g., PD Walks), and participation in PD-associated speaking engagements. San Diego contains a tight-knit community of professionals who work together to better serve individuals with PD and numerous people have expressed their support of this study.

10.1b) Non-Veterans must be given a copy of the VA Notice of Privacy Practices (NOPP) and sign the acknowledgement form. The Privacy Officer must be notified when a non-Veteran is enrolled in the study and be provided with a copy of the signed NOPP. If CPRS notes are entered, and the acknowledgement must also be scanned into CPRS. The NOPP, Acknowledgement form, and instructions to provide the completed form to the PO are available under the ? at the top right corner of this page.

Agree Disagree

Section 10.5 Individuals with Cognitive/Decisional Impairment

10.5) Provide the rationale and additional study procedures that will be required for including individuals with known cognitive impairment or institutionalized individuals. Address Decisional Capacity Assessment and Surrogate Consent Sections 12.6 and 12.7.

Phase I:

If participant lacks capacity to complete neuropsychological assessments, they will be thanked for their time and excused from the research study.

Phase II:

If a subject meets criteria for our study and is interested in participating, an appointment will be made to enroll the individuals in the study. Informed consent will be obtained at the time of visit. When the subject arrives for the appointment, a verbal explanation of the protocol will be given by the Principal Investigator or a member of the research team. A post-consent quiz will also be administered to ensure adequate understanding of the key elements of the study. If the subject performs adequately on the post-consent questionnaire, they will be asked to sign the consent form. If the subject is unable to demonstrate capacity to sign the consent form, they will be thanked for being a possible subject in the study and

excused from the rest of testing. Given that we will be recruiting nondemented PD patients, it is not anticipated that any patients will be unable to consent.

Similarly, for individuals participating in the adjunct programs, informed consent will be obtained at the time of visit. When the subject arrives for the appointment, a verbal explanation of the adjunct programs will be given by the Principal Investigator or a member of the research team. A post-consent quiz will also be administered to ensure adequate understanding of the key elements of this portion of the study. If the subject performs adequately on the post-consent questionnaire, they will be asked to sign the consent form. If the subject is unable to demonstrate capacity to sign the consent form, they will be thanked for being a possible subject in the study and excused from the rest of testing. Given that we will be recruiting nondemented PD patients, it is not anticipated that any patients will be unable to consent.

Section 11 - Recruitment

11) Describe, step-by-step, the plans for recruitment of subjects (or selection of subjects as in record review). This description must include how, when, and where potential subjects are approached as well as procedures for identifying potential participants (through medical records, physician referral, third-party sources, etc.). Include how selection is equitable. Indicate if vulnerability to coercion may be present and if so plans to ensure voluntary participation.

Phase I:

At the time of their clinical or research visit in which they are identified as having PD with cognitive impairment and/or dementia, participants meeting inclusion criteria for this study will be approached about their interest in participating in the study. Potential participants will be informed of the study via a flyer (appended) and, if requested, study coordinators (e.g., [name]. or any co-investigator affiliated with the study) will contact the individual to explain the study procedures and answer any questions the potential participant may have.

We will also recruit patients by placing announcements in local newsletters sent out by various Parkinson's disease support groups (e.g., the Parkinson's Disease Association of San Diego) and advertisements in the local media calling for potential research participants. The same wording as in the handout will be used for these announcements, except the phrase "You have been given this handout because you may be interested in participating in this study" will be removed.

